### **2.6.2.1.1 Handling of missing values/censoring/discontinuations**

For the calculation of the win-ratio an initial time “at risk” (follow-up) for each subject will be calculated as number of days from treatment start date to their attained:

- Date of last visit (End of Study visit)
- Date of death from any cause
- Date of withdrawal of informed consent
- Date of loss to follow up

### **CV death events**

In the case of CV death in one or both subjects the following censoring rules will be applied:

- If a CV death occurs in both subjects then all time at risk will be considered and the subject with the latest time to CV death will be considered the winner
- If a CV death occurs in one subject and it occurs before the second subject time at risk is censored then the subject who does not experience the CV death will be considered the winner

- If a CV death occurs in one subject and it occurs after the second subject time at risk is censored then the pair will be considered a tie

Note: for this event deaths from non-CV causes will be censored.

### **HF hospitalization events and urgent HF visits**

For these events only those that occur in the time at risk that is common for both subjects in the pair will be used for analysis to define win or tie. For example, if subject 1 of a pair has 145 days at risk and subject 2 has 126 days only events that occur days 1-126 are considered.

### **Time-averaged proportional change in NT-proBNP (from baseline to Weeks 4 and 8)**

If the NT-proBNP value is missing for one or both subjects in the pair then the pairwise comparison of the change in NT-proBNP is considered tied.

#### **2.6.2.1.2 Sensitivity Analysis:**

Three sensitivity analyses are planned for secondary endpoint 1.

- The primary analysis of the win ratio will be repeated but will also include HF hospitalizations that are adjudicated as Possible HF Hospitalization (i.e. are insufficient data to meet PARAGLIDE-HF criteria) in addition to confirmed HF hospitalizations.
- The primary analysis of the win ratio will be repeated but data for CV death, HF hospitalizations and urgent HF visits will be based on investigator reporting and not adjudicated data.
- The primary analysis of the win ratio will be repeated but data that occurs after diagnosis as COVID-19 positive will be censored at the subject level.

#### **2.6.2.2 Analysis of secondary endpoint 2**

The cumulative number of recurrent composite events over time, i.e., the total number of composite events of

- a) CV death (Adjudicated by EAC),
- b) HF hospitalizations (Adjudicated by EAC - only the confirmed events will be considered, i.e. HF hospitalizations meeting PARAGLIDE-HF criteria),
- c) Urgent HF visits (Adjudicated by EAC),

The FAS will be used in the main analysis of the secondary endpoint 2.

The cumulative number of composite events, ie, the total number of composite events of CV death, recurrent HF hospitalizations, and recurrent urgent HF visits for a subject over time will be calculated. The time to these recurrent events will be analyzed using the semi-parametric proportional rates model (abbreviated as LWYY model)([Lin 2000](#)). The hypotheses of interest are:

H30: Rate ratio of sacubitril/valsartan arm over valsartan arm equal to 1, versus

H3a: Rate ratio of sacubitril/valsartan arm over valsartan arm not equal 1.

A rate ratio < 1 indicates an effect in favor of sacubitril/valsartan arm.

The hypothesis (H30) will be tested, and 95% CIs will be provided. The rate ratio will be estimated from the above proportional rates model with treatment and in-hospital/out-of-hospital randomization as fixed factors through maximization of a partial likelihood score function. The CIs will be based on the robust estimate of the standard errors. The number and percentage of CV events by event type will be summarized.

*Censoring Variables:*

The CV death will not be considered a censoring variable, but a composite endpoint event and a conditional factor in this analysis. Time to non-CV death will be considered as a censoring variable. Any censoring due to non-CV death is assumed to be non-dependent in the analysis.

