HFpEF patients with ADHF are known to have markedly elevated levels of BNP and NT-proBNP, which are reduced following adequate treatment and normalization of their cardiac decompensation. In the I-PRESERVE trial, patients with both a recent hospitalization and elevated NT-ProBNP ($>$ 360 pg/mL) had a greater risk of cardiovascular death and subsequent heart failure hospitalization ([Kristensen et al 2015](#)). Therefore, it is important to evaluate therapeutic strategies that can lead to superior reductions in NT-proBNP in patients hospitalized due to acute decompensation.

The PIONEER-HF trial evaluated the effect of in-hospital initiation of sacubitril/valsartan vs. enalapril in patients with heart failure with reduced ejection fraction (HFrEF) who had been stabilized during hospitalization for acute decompensated heart failure. PIONEER-HF demonstrated greater reduction with sacubitril/valsartan vs. enalapril in time-averaged proportional change in NT-ProBNP from baseline to weeks 4 and 8 (percent change, -46.7% vs. -25.3%; ratio of change with sacubitril/valsartan vs. enalapril 0.71 [0.63 – 0.81], $p<0.001$) and a decrease in the exploratory clinical composite outcome of death, re-hospitalization for heart failure, LVAD implantation, or listing for cardiac transplant ([Velazquez et al 2018](#)).

Based on the above, PARAGLIDE-HF is designed to assess the efficacy, safety and tolerability of sacubitril/valsartan in HFpEF patients with a WHF event (HFpEF decompensation) who have been stabilized and initiated at the time of or within 30 days post-decompensation.

These data from PARAGLIDE-HF will complement TRANSITION and PIONEER-HF, where both examined the safety and efficacy of sacubitril/valsartan in hospitalized patients hemodynamically stabilized after an acute decompensated HFrEF event ([Wachter R et al 2018](#), [Velazquez et al 2018](#)).

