8.3.3 Biomarkers

BNP or NT-proBNP will be measured in all patients by using the local laboratory at Visit 1 to determine eligibility. NT-proBNP will be measured in all patients using the central laboratory at Visits 2 (randomization), 3, 5, and 7 (Weeks 0, 1, 4, and 8 respectively).

During the COVID-19 pandemic that limits or prevents on-site study visits, or if visits by site staff to a participant's home are not feasible, the collection of standard chemistry and hematology samples may be modified by Novartis and will be communicated to the Investigator. For the primary endpoint biomarkers (Weeks 4 and 8), alternative methods of collecting and ensuring shipment of biomarkers to the central laboratory should be implemented. Alternative methods must comply with guidance issued by local regulatory bodies and be discussed with Novartis.

Evaluation of neprilysin measurement at baseline as a predictor of clinical outcome may be added depending on availability of a validated assay and sample handling requirements. The list may be changed or expanded further as new relevant biomarkers may be discovered during this study and after its completion. As such, serum and plasma will be bio-banked for analysis of yet to be identified diagnostic biomarkers. Details of sample collection, handling and shipment will be provided to investigators in the laboratory manual.

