The cumulative number of composite events, i.e., the total number of composite events of CV death, recurrent HF hospitalizations, and recurrent urgent HF visits for a patient over time will be calculated. The time to these recurrent events will be analyzed using the semi-parametric proportional rates model (abbreviated as LWYY model) ([Lin et al 2000](#)). The hypotheses of interest are:

H_{30} : Rate ratio of sacubitril/valsartan arm over valsartan arm equal to 1, versus

H_{3a} : Rate ratio of sacubitril/valsartan arm over valsartan arm not equal 1.

A rate ratio < 1 indicates an effect in favor of sacubitril/valsartan arm.

The FAS will be used in the main analysis of the second key secondary endpoint.

The hypothesis (H_{30}) will be tested and 95% confidence interval will be provided. The rate ratio will be estimated from the above proportional rates model through maximization of a partial likelihood score function and the confidence intervals will be based on the robust estimate of the standard errors. The number and percentage of CV events by event type will be summarized.

The CV death will not be considered as a censoring variable, but as a composite endpoint event and a conditional factor in this analysis. Time to non-CV death will be considered as a censoring variable. Any censoring due to non-CV death is assumed to be non-dependent in the analysis.

Analysis of secondary endpoint 3

The total number of composite events will be analyzed using a negative binomial regression model with the count data as the dependent variable. Treatment group and in/out-of-hospital randomization as a fixed-effect factors and log (follow-up duration) as the off-set. The model will be used to estimate event rates and their 95% confidence intervals by treatment group.

The time to the first composite event will be analyzed using Cox's proportional hazard model with factors treatment and in/out-of-hospital randomization. Hazard ratio for treatment and its 95% confidence interval will be reported.

Analysis of secondary endpoint 4

The proportional change in NT-proBNP from Baseline to Week 8 will be analyzed using an ANCOVA model similar to that of the primary efficacy analysis.

Analysis of secondary endpoint 5

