The first amended protocol (Amendment 01) extended duration of treatment from 12 weeks (Original Protocol) to a maximum of approximately 20 months, and increased the sample size to 800 subjects. The average duration of study for all participants was anticipated to be approximately 11 months based in modeling from December 2019.

With Protocol Version 01 (Amendment 01) and subsequent amendments, all participants will be in double-blind treatment throughout the study, and there is no open label treatment phase.

Protocol Version 00 (Original Protocol) includes participants who signed Informed Consent and were randomized prior to execution of Protocol Version 01 (Amendment 1). Some of these participants already have completed the full 8 week double-blind period and have either finished or already commenced the 4 weeks open-label period; these participants were not eligible for continuation into Amendment 1, although their data is eligible for inclusion with all participants.

Another subset is those participants who were randomized to Protocol Version 00 who are still active in the 8 week double-blind period, and have not entered the open-label period.

If these participants are interested and can provide their voluntary signature to the revised Informed Consent prior to completion of the double-blind period, these participants would be eligible to continue in Amendments 01, 02, 03 and 04 with no open-label period. Lastly, those participants randomized subsequently to Institutional Review Board approval of Amendments 01, 02, 03, and 04 and the appropriate Informed Consent for the amended protocols would enter directly into the protocol as defined in the respective amended protocols.

Throughout all protocol versions, the primary endpoint remains the time-averaged proportional change in N-terminal pro-brain natriuretic peptide (NT-proBNP) from Baseline to Weeks 4 and 8. The most recent protocol amendment (Amendment 04) changed the sample size to 450 subjects with 85% power, deemphasizing the statistical power for key secondary clinical endpoints, however clinical events will still be assessed as secondary endpoints.

[Section 1.2](#) shows the most recent version of the study objectives and endpoints according to protocol Amendment 04.

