### 2.2.1 Subgroups of interest

The following subgroups will be analyzed for the primary endpoint and for selected secondary endpoints based on clinical decision:

1. Age group ( $< 65, \geq 65$  years) and ( $< 75, \geq 75$  years)
2. Left ventricular ejection fraction (LVEF) categories prior to randomization:
  - $> 40$  to  $< 45\%$  vs.  $\geq 45\%$ ;

- > 40 to < 50% ((HFmrEF (mildly reduced) ), ≥ 50% ( (HFpEF) preserved )
- ≥ 50 to ≤ 60% vs. >60\*
- >40 to ≤60 vs. > 60\*
- ≤ median vs. > median

3. Prior use of ACEi/ARB (at the time of hospitalization)
4. Four groups defined by the Baseline quartiles of NT-proBNP
5. Baseline eGFR (< 45, 45 to < 60, ≥ 60 ; <30 or ≥ 30 mL/min/1.73 m^2)
6. SBP at randomization (< 110, ≥ 110 mm Hg)
7. Race
8. Ethnicity
9. Atrial fibrillation (AF) vs. no AF at the time of consent
10. Body mass index (BMI) ≥ 30 vs. BMI < 30; BMI ≤50 vs. >50 kg/m^2
11. Sex
12. New onset HF (at the time of hospitalization) – ‘de novo heart failure’
13. New York Heart Association (NYHA) class at randomization
14. Recovered EF / Improved EF (HFimpEF) (most recent left ventricular ejection fraction (LVEF) > 40% (within past 3 months), but history of prior documented LVEF < 40%)
15. Time from presentation to hospital (if applicable) to randomization time
16. Prior history of HF
17. Prior Hospitalization for Heart Failure
18. Duration of Heart Failure (< 12 months, 12-24 months, 24-60 months, and > 60 months)
19. In-hospital/out-of-hospital randomization status
20. Structural heart disease (yes/no)
21. Subjects without COVID-19 positive during the trial.
22. Enrollment Country: Canada vs United States

\* LVEF of >60% is defined as normal; LVEF <= 60% is defined as “below normal”

See [Sections 2.5](#) and [2.6](#) for further details on the primary and secondary objectives, respectively.

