##### **Estimand 1**

Population: Defined through the appropriate inclusion/exclusion criteria to reflect the targeted study population currently hospitalized for or within 30 days of a WHF event (HFpEF decompensation). A WHF event (HFpEF decompensation) is defined as a hospitalization, emergency department (ED) visit or out-of-hospital urgent HF visit, all requiring IV diuretics.

Endpoint: Time-averaged proportional change between Baseline and weeks 4 and 8 in NT-proBNP

Treatment: The randomized treatment sacubitril/valsartan or valsartan

Intercurrent event: Using a treatment policy strategy to handle the intercurrent event of treatment discontinuation.

Summary measure: Difference between treatment in ratios of geometric means

The primary null hypothesis to be tested is the ratio of the geometric means of NT-proBNP (average of Weeks 4 and 8 divided by Baseline) for the sacubitril/valsartan and valsartan treatment groups are equal ( $H_{10}$ ) versus the alternative hypothesis that the ratio of the geometric means of NT-proBNP are not equal ( $H_{1a}$ ).

For NT-proBNP, the time-averaged proportional change from Baseline in a natural logarithmic scale will be analyzed using an ANCOVA model using data from Weeks 4 and 8 with treatment,

in-hospital/out-of-hospital randomization status, gender, and Baseline LVEF ( $\leq$  Median,  $>$  Median) as fixed effect factors, age and the logarithmic Baseline NT-proBNP as covariates.

The values from Weeks 4 and 8 will be averaged and the change from Baseline in log transformed NT-proBNP will be calculated as follows:

$$\ln(\text{average post dose value}) - \ln(\text{baseline value})$$

The estimated treatment effect in terms of ratios of geometric means, based on the least-squares (LS) means from the model, and the corresponding two-sided 95% confidence intervals (CIs) will be presented.

The geometric means (presented as a ratio to Baseline) will be calculated by exponentially back transforming the LS means based on the ANCOVA model as follows:

$$\exp(\text{LS mean})$$

The FAS will be used for the primary endpoint analysis.

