Under the proportional rates model, the individual rate function for the composite endpoint of CV death and total HF hospitalizations is assumed to be,  $\lambda_i(t, x_i) = Y_i(t)\lambda_0(t)\exp(\beta_0 x_i)$ , where  $Y_i(t) = 1$  if subject  $i$  is at risk for CV death, recurrent HF hospitalizations, and recurrent urgent HF visits at time  $t$  and  $\lambda_0(t) = 0$  if subject  $i$  is censored or died from a CV reason at time  $t$

The primary hypothesis to be tested is,  $H_{30}: \beta_0 = 0$  versus  $H_{3a}: \beta_0 < 0$ , where  $\exp(\beta_0)$  is the relative risk or rate ratio of CV death, recurrent HF hospitalizations, and recurrent urgent HF visits in the sacubitril/valsartan group relative to the valsartan group given the subject has not died from a CV reason at time  $t$ , which is assumed to be constant over time .

The primary hypothesis could be equivalently written as:

$H_{30}$ : Rate ratio (sacubitril/valsartan)/(valsartan) = 1

versus

$H_{3a}$ : Rate ratio (sacubitril/valsartan)/(valsartan) < 1,

A rate ratio < 1 indicates an effect in favor of sacubitril/valsartan.

The rate ratio and its 95% CI will be estimated from the above proportional rates model through maximization of a partial likelihood score function. The resulting estimate of  $\exp(\beta_0)$  is identical to the one described by Anderson and Gill (1982), but unlike Anderson-Gill, a robust variance

estimator (sandwich estimator) is used to account for the dependency of within subject events. The number and percentage of CV events by event type will be summarized.

The LWYY analysis can be carried out using the following SAS code:

```
proc phreg data=primary_data covs(aggregate);  
  model (time_start, time_rec)*status_rec(0)=treat/ties=efron rl;  
  id usubjid;  
run;
```

where primary\_data is the input dataset, time\_start is the previous event stop time and time\_rec is the current event stop time, the censoring variable status\_rec (0 for censored and 1 for event) should take the value 1 if the last event is a CV death and 0 if it is censored for any non-CV death reasons for the given subject; usubjid is the subject ID.

As a supportive part of the analysis, the two components in the composite endpoint (recurrent HF hospitalizations, and recurrent urgent HF) will be analyzed separately to quantify the respective treatment effects and check the consistency between the composite and the components.

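### The total-events model for CV death, HF hospitalization and urgent HF visits leaves out log baseline NT-proBNP: the planned test is valid but gives up a small amount of precision, and the SAP's code does not match its text

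*SAP*

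**What the plan says.** SAP 2.6.2.2 analyses the recurrent composite with a semi-parametric proportional rates (LWYY) model and robust standard errors. The rate ratio is "estimated from the above proportional rates model with treatment and in-hospital/out-of-hospital randomization as fixed factors". None of the four sensitivity analyses in 2.6.2.2.1 adds a baseline covariate.

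The other descriptions of the model differ. The SAP 5.4.3 code reads "model (time_start, time_rec)*status_rec(0)=treat/ties=efron rl", which is treatment alone, and the rate function written there also has only the treatment term. Protocol 12.5.1 names no covariate: "The rate ratio will be estimated from the above proportional rates model through maximization of a partial likelihood score function".

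On baseline NT-proBNP:
- **Collection.** Protocol 8.3.3: "NT-proBNP will be measured in all patients using the central laboratory at Visits 2 (randomization), 3, 5, and 7".
- **Primary model.** SAP 2.5.2 (Estimand 1) includes "age and the logarithmic Baseline NT-proBNP as covariates".
- **Prognosis.** Protocol 1.1 reports from an earlier HFpEF trial that patients with both a recent hospitalization and NT-proBNP above 360 pg/mL "had a greater risk of cardiovascular death and subsequent heart failure hospitalization".
- **Clinical endpoints.** It appears only as a subgroup factor, "Four groups defined by the Baseline quartiles of NT-proBNP", for those secondary endpoints that are selected (SAP 2.2.1).

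Amendment 4 cut the sample from 800 to 450. SAP 1.1 describes this as "deemphasizing the statistical power for key secondary clinical endpoints".

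**The concern.** An event model with robust standard errors gains precision from a baseline variable that predicts the event. The protocol's own background says NT-proBNP predicts two of the three components, and the primary analysis already derives its logarithm. Leaving it out keeps explainable variation in the standard error of the log rate ratio. It also leaves any chance difference between arms in baseline NT-proBNP unadjusted, in a trial with no stratified randomization (SAP 1.1).

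What is at stake is the width of the confidence interval for the trial's total-events result, on an endpoint that Amendment 4 left with reduced power. Separately, a programmer following 5.4.3 would fit a different model from the one in 2.6.2.2.

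**Working it through.** **1. The plan's own power figure.** The documents give power for the primary endpoint only. With 450 × 0.85 / 2 = 191.25 evaluable patients per arm, a difference of 0.2614 and SD 0.85, z = 0.2614 / (0.85 × √(2/191.25)) = 3.007. Power is Φ(3.007 − 1.96) = 0.8525, against the stated 85%. It reproduces. No power, event count or effect size is stated for the total-events endpoint.

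**2. Inputs for the total-events endpoint.**
- Control rate: 26.7 per 100 patient-years, valsartan patients hospitalized within 30 days (Protocol 1.1).
- Rate ratio: (26.7 − 6.4)/26.7 = 0.76. This reads the 6.4% absolute reduction in Protocol 1.1 as a rate difference, which is an assumption.
- Follow-up: 11 months on average (Protocol section 3).
- Size: 225 per arm.

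**3. Events and an upper bound on power.** Expected events = 225 × (11/12) × 0.267 × (1 + 0.76) = 96.9. If events were independent, power would be Φ(½√96.9 × |ln 0.76| − 1.96) = Φ(1.351 − 1.96) = 0.27. At a rate ratio of 0.87 there would be 103 events and power of about 0.105.

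**4. Effect of the covariate, by simulation.** There were 3,000 trials per setting, with follow-up uniform from 2 to 20 months (mean 11) and gamma frailty variance 1 or 2 (assumed). A log-rate model with robust variance stood in for LWYY. It was fitted with treatment alone and with treatment plus a standardized baseline covariate. The rate ratio per SD of the covariate is assumed, because the documents give none.

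Results at a true rate ratio of 0.76:

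| Rate ratio per SD | Frailty variance | Variance reduction | Power without → with |
|---|---|---|---|
| 1.25 | 1 | 0.0% | 23.1% → 23.6% |
| 1.5 | 1 | 2.3% | 21.0% → 22.7% |
| 1.75 | 1 | 4.5% | 19.2% → 21.0% |
| 2.0 | 1 | 8.8% | 20.1% → 21.7% |
| 1.25 | 2 | 1.4% | 19.5% → 19.6% |
| 1.5 | 2 | 2.3% | 19.7% → 20.5% |
| 1.75 | 2 | 4.0% | 17.8% → 18.8% |
| 2.0 | 2 | 7.5% | 16.3% → 17.5% |

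If the covariate has no association with events (1.0 per SD), the change in variance is −0.4%, so a useless covariate costs almost nothing. The mean estimated rate ratio is the same to within 0.002 with and without the covariate.

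**5. Validity.** At a true rate ratio of 1, rejection rates were 4.9-6.5% without the covariate and 5.0-6.0% with it.

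**6. Chance imbalance.** The difference between arms in a standardized covariate has standard error √(2/225) = 0.094 SD, so a 1-in-20 imbalance is 1.96 × 0.094 = 0.185 SD. It would multiply the estimated rate ratio by exp(0.185 × ln r), where r is the rate ratio per SD: 1.04, 1.08, 1.11 and 1.14 for r = 1.25, 1.5, 1.75 and 2.0, or the reciprocals. The confidence interval already allows for this. Adjustment removes it from the single estimate that will be read.

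**7. Missing baselines.** If 5% of patients (illustrative) were dropped for want of a baseline value, variance would rise by a factor of about 1/0.95 = 1.05. That cancels the gain for covariate rate ratios up to about 1.75 per SD, so the missing-value rule matters.

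**The case against.** The strongest reply is that nothing is broken. Treatment is randomized, the robust test is valid without the covariate, and treatment plus in/out-of-hospital status is also the set used for secondary endpoints 3 and 7, so the choice is consistent. The endpoint is secondary, with nominal p-values and no multiplicity adjustment (SAP 2.6.1), and Amendment 4 openly accepted reduced power. One covariate does not repair that. All of this stands, and it limits the point to an optional improvement.

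Three further limits also stand:
- **The prognostic evidence is indirect.** The Protocol 1.1 statement combines recent hospitalization with a 360 pg/mL cut-off and does not name urgent HF visits. Entry already requires at least 500 pg/mL (1000 in AF) or a BNP equivalent. In-hospital patients may qualify on a local value at decompensation, and levels fall with treatment, so Visit 2 values are not truncated at 500. The slope among enrolled patients is still unknown.
- **The simulated comparison starts from treatment alone.** That is the 5.4.3 code. If in/out-of-hospital status shares prognostic information with NT-proBNP, the gain over the 2.6.2.2 model is smaller.
- **Baseline values may be missing.** SAP section 3 allows 15% missingness at baseline or at both later visits and does not give the baseline share. The missing-value rule below answers this without dropping anyone.

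A reader might infer that the omission biases the rate ratio or inflates type I error. It does neither: imbalance is random over repeated trials. A reader might also infer a larger gain. At 0.4 events per year and a true rate ratio of 0.65, power would rise by about 1 to 7 points. Neither input is in the documents. Protocol 1.1 gives 26.7 per 100 patient-years. The urgent visits it does not name could raise that somewhat, but nothing supports 0.65.

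SAP section 2.12 is not visible in the public text, so an adjusted analysis there can be neither confirmed nor excluded.

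**Conclusion.** The omission is real and minor. Neither the text of SAP 2.6.2.2 nor the model and code in 5.4.3 uses log baseline NT-proBNP, and the code also drops the in/out-of-hospital factor that the text requires.

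On rates taken from the protocol, adjustment would lower the variance of the log rate ratio by about 0-9% and add about 0-2 points of power. The estimate itself would hardly move. This rests on the reading of the 6.4% reduction as a rate difference, assumed frailty variances of 1 and 2, assumed covariate rate ratios of 1.25 to 2.0 per SD, and a constant-rate stand-in for LWYY that does not model CV death as ending follow-up. The endpoint stays underpowered either way. The change is worth making because it costs so little and the same lines of the SAP need reconciling anyway.

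**What to change.** Before database lock:

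1. Add log baseline NT-proBNP as a covariate to the LWYY model in SAP 2.6.2.2.
2. Make the model and code in 5.4.3 match, with treatment, in/out-of-hospital status and log baseline NT-proBNP.
3. Prespecify that a missing baseline value is replaced by the mean of the log values, with a missing indicator in the model, so that every FAS patient stays in the analysis.
4. Report the model with treatment and in/out-of-hospital status alone as a sensitivity analysis.

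The cost is one more model term, plus the indicator where values are missing, using a variable the primary analysis already derives. The rate ratio becomes conditional on baseline NT-proBNP, and the report should say so.
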